### **1.3. Schedule of Activities (SoA)**

This section includes the following SoAs:

- Baseline, On-Study and Post-Study Treatment Follow-Up SoA
- Continued Access SoA

Baseline, On-Study and Post-Study Treatment Follow-up SoA														
	Baseline		Cycle = 21 days							Short-Term Follow Up a			Long-Term Follow-Up b	Instructions
	(Day Relative to C1D1)		Cycle 1				Cycle 2		Cycle 3-n	801	802	803	804-X	
			(±3 days)				(±3 days)		(±3 days)	30 day follow-up ±5 days	60 day follow-up ±5 days	90 day follow-up ±5 days	Q90D	
Procedure	≤28	≤7	D1	D2	D8	D15	D1	D2	D1					
Informed consent (Main and Phase 1b Cohort C consent)	X													Main ICF must be signed before any protocol-specific procedures are performed and Phase 1b Cohort C ICF prior to tissue collection for CD73 testing
Inclusion/exclusion criteria	X													
Medical history	X													Including assessment of preexisting conditions and historical illnesses, and habits (such as tobacco and alcohol use).
Cancer treatment history	X													Record prior anticancer therapy
Concomitant medication	X		X							X	X	X		See Section 6.5
Physical examination	X		X		X	X	X		X					Collect weekly during Cycle 1, and then on D1 of every cycle thereafter. A partial physical examination may be performed by a healthcare professional other than the physician on C1D8 and C1D15.
Vital signs	X		See Section 1.3.1.						X	X				Collect weekly during Cycle 1, and then on D1 of every cycle thereafter. Please collect vitals as follows: - At baseline only: Height, - At D1 of every cycle: Weight, - At every schedule visit: Temperature, blood pressure, pulse rate, respiratory rate, and pulse oximetry. Please refer to Section 1.3.1. for detailed collection pertaining to collection on C1D1-C3-n (D1).

Baseline, On-Study and Post-Study Treatment Follow-up SoA															
	Baseline		Cycle = 21 days							Short-Term Follow Up a			Long-Term Follow-Up b	Instructions	
	(Day Relative to C1D1)		Cycle 1				Cycle 2		Cycle 3-n	801	802	803	804-X		
			(±3 days)				(±3 days)		(±3 days)	30 day follow-up ±5 days	60 day follow-up ±5 days	90 day follow-up ±5 days	Q90D		
Procedure	≤28	≤7	D1	D2	D8	D15	D1	D2	D1						
AE collection	X								X					Collect continuously at every visit and throughout the study using CTCAE Version 5.0. During the 30-, 60-, and 90-day follow-up visits, collect all AEs/SAEs. Thereafter, collect only SAEs related to study treatment or protocol procedures	

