### 6.1.1. Definition of DLT and DLT-ET

#### 6.1.1.1. DLT

A DLT is defined as any of the events listed in the table below, if both of the following criteria are met:

- the event occurs during the DLT observation period (28 days) in Phase 1a, and
- the event cannot, in the opinion of the investigator, be definitely attributed to primary disease or extraneous causes, such as accident.

Patients who experience a DLT in the DLT observation period will be discontinued from study treatment.

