### **8.3. Adverse Events and Serious Adverse Events**

Investigators are responsible for monitoring the safety of participants who have entered this study and for alerting Lilly or its designee to any event that seems unusual, even if this event may be considered an unanticipated benefit to the participant.

The investigator is responsible for the appropriate medical care of participants during the study.

Investigators must document their review of each laboratory safety report.

The investigator should provide AE verbatim terms and then the terms will be mapped by Lilly or its designee to corresponding terminology within the Medical Dictionary for Regulatory Activities (MedDRA) Lower Level Term (LLT) dictionary. The investigator will use Common Terminology Criteria for Adverse Events (CTCAE) version 5.0 to assign AE severity grades.

The investigator remains responsible for following, through an appropriate health care option, AEs that are serious or otherwise medically important, considered related to the investigational product or the study, or that caused the participant to discontinue the investigational product before completing the study. The participant should be followed until the event resolves, stabilizes with appropriate diagnostic evaluation, or is otherwise explained. The frequency of follow-up evaluations of the AE is left to the discretion of the investigator.

Lack of drug effect is not an AE in clinical studies, because the purpose of the clinical study is to establish treatment effect.

After the ICF is signed, study site personnel will record via CRF the occurrence and nature of each participant's preexisting conditions, including clinically significant signs and symptoms of the disease under treatment in the study. In addition, site personnel will record any change in the condition(s) and any new conditions as AEs. Investigators should record their assessment of the potential relatedness of each AE to protocol procedure, investigational product, via CRF.

The investigator will interpret and document whether or not an AE has a reasonable possibility of being related to study treatment, study device, or a study procedure, taking into account the disease, concomitant treatment or pathologies.

A “reasonable possibility” means that there is a cause and effect relationship between the investigational product, study device and/or study procedure and the AE.

The investigator answers yes/no when making this assessment.

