### **Suspected Unexpected Serious Adverse Reactions**

Suspected unexpected serious adverse reactions (SUSARs) are serious events that are not listed in the IB and that the investigator identifies as related to investigational product or procedure. United States 21 CFR 312.32 and European Union Clinical Trial Directive 2001/20/EC and the associated detailed guidances or national regulatory requirements in participating countries require the reporting of SUSARs. Lilly has procedures that will be followed for the identification, recording and expedited reporting of SUSARs that are consistent with global regulations and the associated detailed guidances.

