#### **8.3.1. Time Period and Frequency for Collecting AE and SAE Information**

Although all AEs after signing the ICF are recorded by the site in the CRF/electronic data entry, SAE reporting to Lilly begins after the patient has signed the ICF and has received study treatment. However, if an SAE occurs after signing the ICF, but prior to receiving study treatment, it needs to be reported ONLY if it is considered reasonably possibly related to study procedures.

Medical occurrences that begin before the start of study intervention but after obtaining informed consent will be reported on the adverse events CRF.

All SAEs will be recorded and reported to the sponsor or designee immediately and under no circumstance should this exceed 24 hours. The investigator will submit any updated SAE data to the sponsor within 24 hours of it being available. Serious adverse events, including death, caused by disease progression should not be reported unless the investigator deems them to be possibly related to study treatment.

Investigators are not obligated to actively seek AEs or SAEs after conclusion of the study participation. However, if the investigator learns of any SAE, including a death, at any time after a participant has been discharged from the study, and he/she considers the event to be reasonably related to the study intervention or study participation, the investigator must promptly notify the sponsor.

Care will be taken not to introduce bias when detecting AEs and/or SAEs. Open-ended and non-leading verbal questioning of the participant is the preferred method to inquire about AE occurrences.

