### 9.4.4. Safety Analyses

All patients who receive at least 1 dose of any study therapy will be evaluated for safety and toxicity.

The MedDRA Version 22.0 (or higher) will be used when reporting AEs by MedDRA terms. The MedDRA Lower Level Term (LLT) will be used in the treatment-emergent computation. Treatment-emergent adverse events will be summarized by System Organ Class (SOC) and by decreasing frequency of Preferred Term (PT) within SOC.

Safety analyses will include summaries of the following:

- DLTs at each DL in the dose escalation phase and DLT-equivalent AEs for expansion cohorts;
- AEs, including severity and possible relationship to study drug;
- SAEs, including possible relationship to study drug;
- AEs leading to dose adjustments;
- discontinuations from study treatment due to AEs or death;
- treatment emergent abnormal changes in laboratory values;
- treatment emergent abnormal changes in vital signs and ECGs.

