6.9.2. Adverse Events

Adverse event (AE) verbatim terms will be provided by the investigators and then will be mapped by Lilly or its designee to corresponding terminology within the Medical Dictionary for Regulatory Activities (MedDRA) Lower Level Term (LLT) dictionary Version 22.0 (or higher).

The investigator will use Common Terminology Criteria for Adverse Events (CTCAE) Version 5.0 (NCI 2009) to assign AE severity grades.

Preexisting conditions are defined as AEs that begin but do not resolve prior to the first dose of study drug in each study period. Preexisting conditions will be presented by patient and can be combined with the listing of AE, so that the history of the preexisting conditions/AEs can be traced.

A treatment emergent adverse event (TEAE) is defined as any AE that begins on or after the day of first dose in the reporting study period or any preexisting condition that increases in CTCAE grade on or after the day of first dose in the reporting study period. The MedDRA LLT will be used in the treatment-emergent computation.

The number of patients who experienced a TEAE, or TEAE possibly related to study drug, will be summarized. Treatment-emergent adverse events will be summarized by System Organ Class (SOC), by Preferred Term (PT) of decreasing frequency within SOC, and by maximum CTCAE grade and grade categories (any, Grade 3 or higher).

Adverse events leading to dose adjustments, treatment discontinuation, or death will also be summarized.

Dose-limiting toxicities in Phase 1a and DLT-equivalent toxicities occurring after Cycle 2 in Phase 1a or any cycle in Phase 1b will be summarized by cohort.

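### Protocol Section 8.3 defines a reasonable possibility of relatedness as actual causation, so related events may be under-attributed and some SAEs after the 90-day visit may go uncollected

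*Protocol*

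**What the plan says.** Protocol Section 8.3 has the investigator record the potential relatedness of each AE. The question is "whether or not an AE has a reasonable possibility of being related to study treatment", a study device or a study procedure, taking the disease and other treatment into account. The next sentence explains that a reasonable possibility "means that there is a cause and effect relationship between the investigational product, study device and/or study procedure and the AE". The answer is yes or no, with no category in between. Neither document defines the term anywhere else.

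The outputs that use relatedness are worded differently:

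- Protocol Section 9.4.4, repeated in SAP Section 6.9, lists "AEs, including severity and possible relationship to study drug".
- SAP Section 6.9.2: "The number of patients who experienced a TEAE, or TEAE possibly related to study drug, will be summarized".
- SAP Section 6.9.3 summarises SAEs whatever their cause, then repeats the summary for those the investigator deems related.
- The SUSAR paragraph in Protocol Section 8.3 covers "serious events that are not listed in the IB and that the investigator identifies as related to investigational product or procedure".
- The Schedule of Activities in Protocol Section 1.3 requires all AEs and SAEs at the 30-, 60- and 90-day visits. It then says: "Thereafter, collect only SAEs related to study treatment or protocol procedures".
- Protocol Section 8.3.1 says that SAEs "caused by disease progression should not be reported unless the investigator deems them to be possibly related to study treatment".

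**The concern.** A yes/no field carries only the meaning its definition gives it. Here the question sets a possibility standard and the definition sets a causation standard. For an event that could be due to the drug but has not been shown to be, the question leads to yes and the definition leads to no. The tables built from the answer are labelled as possible relationship, so a reader of the study report would not know that a stricter test may have been applied.

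This matters in a first-in-human, open-label study without a data monitoring committee, where the related-event profile of a new agent is being described for the first time. Protocol Section 6.6.2 warns that immune-related events may appear several months after the last dose. That is the period in which causality is hard to affirm, and after the 90-day visit relatedness also decides whether an SAE is collected at all.

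**Working it through.** No sample size, error rate or interval in either document depends on this definition, so there is no figure to reproduce. The check is to set the texts side by side and follow the yes/no answer to each place where it is used.

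**Step 1: the standard each text sets**

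| Place | Standard |
|---|---|
| Protocol 8.3, the question | reasonable possibility |
| Protocol 8.3, the definition | causation exists |
| Protocol 8.3, SAE text (before first dose; after discharge) | reasonably possibly related |
| Protocol 8.3.1, progression SAEs | possibly related |
| Protocol 8.3.5, deaths from study disease | may have been caused by the product |
| Protocol 9.4.4 and SAP 6.9 | possible relationship |
| SAP 6.9.2 | possibly related |
| Protocol 8.3 (SUSARs), Protocol 1.3 (after day 90), SAP 6.9.3 (repeat summary) | related, with no qualifier |

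The definition stands alone against the possibility wording. The three places in the last row carry no possibility wording of their own, so they lean most on whatever Section 8.3 says relatedness means.

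**Step 2: what a literal no does at each use**

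- *Related-TEAE and related-SAE summaries (SAP 6.9.2, 6.9.3).* The event drops out of the related table but stays in the all-causality one. This is under-attribution.
- *SUSARs.* An unlisted serious event that is answered no falls outside the protocol's description of a SUSAR. The risk is missed classification, and with it missed expedited reporting.
- *SAEs after the 90-day visit (Protocol 1.3).* Only related SAEs are collected, so an event answered no may not be collected.

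**Step 3: what the answer does not touch**

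- All AEs after consent go on the CRF, with no causality filter (Protocol 8.3).
- SAEs after first dose are alerted within 24 hours whatever the cause, apart from the progression exception in Protocol 8.3.1 and 8.3.5.
- All AEs and SAEs are collected at the visits up to day 90 (Protocol 1.3).
- TEAEs and SAEs are also summarised regardless of cause (SAP 6.9.2, 6.9.3).
- A listed event in the observation period counts as a DLT if "the event cannot, in the opinion of the investigator, be definitely attributed to primary disease or extraneous causes, such as accident" (Protocol 6.1.1.1). That is the reverse burden of proof. Only the catch-all DLT item speaks of possible relation to treatment.

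**Step 4: direction and size**

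In any arm, let *a* be the number of patients with at least one event whose causation the investigator would affirm, and *b* the number whose suspect events are all plausible but unproven. The possibility standard counts *a* + *b* patients with a related event. The literal definition counts *a*. The shortfall is *b*, which cannot be negative, so the direction is fixed. Neither document gives *b*, or how often investigators would follow the definition rather than the question, so the size cannot be computed.

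**The case against.** The strongest reply is that nobody reads the sentence alone. The same section speaks of potential relatedness and of a reasonable possibility, so an investigator meets a possibility standard before reaching the definition. The after-discharge text, the progression rule and the text on deaths from study disease each carry their own possibility wording. The sponsor receives SAE alerts whatever the cause and states that it has its own procedures for identifying SUSARs. This has force. It makes the harm conditional, and it narrows the collection risk mainly to the long-term follow-up rule in the Schedule of Activities. It does not remove the contradiction: the odd sentence is the only definition given, and it governs a binary answer.

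A reader might infer more than the documents support:

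- *That drug toxicity is under-recorded.* Up to day 90, events are recorded and summarised whatever their cause. What is at risk there is the related label.
- *That the RP2D choice is biased.* Protocol Section 6.1.2 bases it on dose adjustments, AEs, chronic intolerance, PK/pharmacodynamics and irAEs, and does not limit AEs to related ones. Escalation and the backfill pause rule rest on DLTs and DLT equivalents.
- *That the DLT rule is itself inconsistent.* A cautious attribution rule for dose decisions can sit beside an ordinary causality field. A DLT marked as not related still counts as a DLT.

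**Conclusion.** The contradiction in Protocol Section 8.3 is real and should be corrected. If the definition is applied as written, three things may follow: plausible but unproven events are under-attributed in the related-TEAE and related-SAE summaries; some serious unlisted events are not identified as SUSARs; and some SAEs after the 90-day visit are not collected. All three run towards fewer related events.

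The conclusion rests on one assumption, that some investigators follow the definition rather than the question before it. The documents neither confirm nor exclude this. The size of any under-count is unknown, and a numerical range would be invented. Sample size and the dose-escalation figures do not change.

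**What to change.** In the definition in Protocol Section 8.3, replace *there is* with *there may be*, leaving the rest of the sentence as it stands. Use that one definition wherever relatedness is judged: the AE row of the Schedule of Activities in Section 1.3, the SAE and SUSAR text in Section 8.3, Section 8.3.1 and Section 9.4.4, and SAP Sections 6.9.2 and 6.9.3. Carry it into any CRF completion guidance.

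A broader test, such as calling an event related unless causation can be ruled out, is not needed. In advanced cancer treated with a combination, few events can be ruled out, and the related tables would lose their power to discriminate.

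The cost is a small text change and somewhat more events classed as related. No analysis, dose rule or sample size is affected.

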### **Serious Adverse Events**

An SAE is any AE from this study that results in 1 of the following outcomes:

- death
- initial or prolonged inpatient hospitalization
- a life-threatening experience (that is, immediate risk of dying)
- persistent or significant disability/incapacity
- congenital anomaly/birth defect
- important medical events that may not be immediately life-threatening or result in death or hospitalization but may jeopardize the participant or may require intervention to prevent one of the other outcomes listed in the definition above. Examples of such medical events include allergic bronchospasm requiring intensive treatment in an emergency room or at home, blood dyscrasias or convulsions that do not result in inpatient hospitalization, or the development of drug dependency or drug abuse.

All AEs occurring after signing the ICF are recorded in the CRF and assessed for serious criteria. The SAE reporting to the sponsor begins after the participant has signed the ICF and has received investigational product. However, if an SAE occurs after signing the ICF, but prior to receiving investigational product, the SAE should be reported to the sponsor as per SAE reporting requirements and timelines (see Section 8.3.1) if it is considered reasonably possibly related to study procedure.

Study site personnel must alert Lilly or its designee of any SAE within 24 hours of investigator awareness of the event via a sponsor-approved method. If alerts are issued via telephone, they are to be immediately followed with official notification on study-specific SAE forms. This 24-hour notification requirement refers to the initial SAE information and all follow-up SAE information. Participants with a serious hepatic AE should have additional data collected using the CRF.

Pregnancy (during maternal or paternal exposure to investigational product) does not meet the definition of an AE. However, to fulfill regulatory requirements any pregnancy should be reported following the SAE process to collect data on the outcome for both mother and fetus.

Investigators are not obligated to actively seek AEs or SAEs in participants once they have discontinued and/or completed the study (the participant disposition CRF has been completed). However, if the investigator learns of any SAE, including a death, at any time after a participant has been discharged from the study, and he/she considers the event reasonably possibly related to the study treatment or study participation, the investigator must promptly notify Lilly.

### **Suspected Unexpected Serious Adverse Reactions**

Suspected unexpected serious adverse reactions (SUSARs) are serious events that are not listed in the IB and that the investigator identifies as related to investigational product or procedure. United States 21 CFR 312.32 and European Union Clinical Trial Directive 2001/20/EC and the associated detailed guidances or national regulatory requirements in participating countries require the reporting of SUSARs. Lilly has procedures that will be followed for the identification, recording and expedited reporting of SUSARs that are consistent with global regulations and the associated detailed guidances.

#### **8.3.1. Time Period and Frequency for Collecting AE and SAE Information**

Although all AEs after signing the ICF are recorded by the site in the CRF/electronic data entry, SAE reporting to Lilly begins after the patient has signed the ICF and has received study treatment. However, if an SAE occurs after signing the ICF, but prior to receiving study treatment, it needs to be reported ONLY if it is considered reasonably possibly related to study procedures.

Medical occurrences that begin before the start of study intervention but after obtaining informed consent will be reported on the adverse events CRF.

All SAEs will be recorded and reported to the sponsor or designee immediately and under no circumstance should this exceed 24 hours. The investigator will submit any updated SAE data to the sponsor within 24 hours of it being available. Serious adverse events, including death, caused by disease progression should not be reported unless the investigator deems them to be possibly related to study treatment.

Investigators are not obligated to actively seek AEs or SAEs after conclusion of the study participation. However, if the investigator learns of any SAE, including a death, at any time after a participant has been discharged from the study, and he/she considers the event to be reasonably related to the study intervention or study participation, the investigator must promptly notify the sponsor.

Care will be taken not to introduce bias when detecting AEs and/or SAEs. Open-ended and non-leading verbal questioning of the participant is the preferred method to inquire about AE occurrences.

### **8.3.2. Follow-up of AEs and SAEs**

After the initial AE/SAE report, the investigator is required to proactively follow each participant at subsequent visits/contacts. All SAEs, will be followed until resolution, stabilization, the event is otherwise explained, or the participant is lost to follow-up (as defined in Section 7.3).

